3.2 Randomization

Participants were randomized into each arm of each intervention, Tech and Touch, in separate processes.

3.2.1 Tech randomization

Tech randomization was accomplished using a 4-digit random number table generated using Stata version 14.0 which was used as a comparison table against the last four digits of the patient's Medical Record Number (MRN) which was assigned prior to study assignment. A preliminary simulation analysis found that random assignment using this model created appropriately sized groups of 40% and 60%.

Individuals who had access to the Full version of MyChart Bedside prior to enrollment in the study (i.e., those patients who were admitted to the Cancer Center, which was not included as a site, or patients who had used MyChart Bedside during the pilot phase of implementation in which only Full-Tech was available) maintained their Full-Tech status and were excluded from randomization if they were transferred to a unit included in the study.

3.2.2 Touch randomization

The study protocol included a series of robust approaches to randomization. Generally, Touch randomization occurred at consent using the randomizer function in Qualtrics which was used for both consent and survey data collection. The Protocol included a procedure for the assignment of Touch in cases where the patient was checked in after daily census and was not included in the Qualtrics randomization (i.e., due to timing of reconciliation between report pulls and the start of the work day). In those cases, a predefined randomization table was used to assign Touch status.

3.3 Blinding

Both the standard and alternate processes for Touch assignment occurred prior to study consent and therefore the TN, the patient, and the care team were blind to their study assignment at consent. Additionally, at the time of provisioning, both the patient and the nurse that assigned the patient the tablet were blind to Tech assignment. TNs providing the intervention were blind to Tech assignment prior to consent, but not prior to study eligibility assessment.

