5.1.1 Inclusion criteria

Study inclusion criteria were as follows:

1. patient accepted tablet and use of MyChart Bedside;
2. patient was available in their room; and,
3. patient was capable of informed consent.

Only patients who were provisioned with MyChart Bedside were included in the study.

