5.2 Recruitment

The AMC Epic Clarity tables were used to develop a fully identified custom Census Report which provided information on all patients who met the inclusion criteria present in the hospital at midnight of each day. The research team integrated this report with the study database to create a daily list of individuals that had consented, refused, not been provided a tablet, or were eligible for being visited by a TN during TN rounding. This information was used to set up a rounding schedule to visit the rooms of these patients to follow up about study participation as follows:

1. In cases where a patient had not been provisioned and there were no clinical notes detailing a rationale for the withholding of access, members of the research team would approach the nursing team and ask them to make a formal determination about the appropriateness of the tablet for the patient.
2. In cases where a patient was provisioned, the study team would put the patient on the rounding schedule and attempt to recruit them to the study.

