5.2.1 Study enrollment, participation, and remuneration

Eligible identified patients were invited to participate in the study via a link in MyChart Bedside which presented an electronic combined HIPAA authorization and consent form approved by the AMC's Institutional Review Board (IRB) for patients to sign to authorize extraction of identified clinical data. Study staff approached eligible patients to identify their interest in participation. Interested patients were guided to the tab within MyChart Bedside that explained that participation included the following tasks and consent:

1. a survey to be taken immediately upon completing consent (the Admission survey);
2. two surveys that would be taken by phone or via an emailed link;
 - a. The 15-day Post-discharge survey
 - b. The 6-month Post-discharge survey
3. additionally, patients were notified that they may be contacted for up to two telephone interviews: within 21 days of discharge and at approximately 6 months post-discharge. Not all individuals would be invited to participate in these interviews;
4. consent to share their clinical data, including the log files associated with their use of patient portals.

Upon completion of each survey, participants had the option to enter contact information on a separate page for a raffle of a \$100 gift card and for future follow-up for additional surveys and interviews. One gift card was raffled off each week throughout data collection.

Participants were provided the option to request a paper combined HIPAA authorization and consent form to sign, delivered by a study team member. Participants received an electronic copy of the signed combined HIPAA authorization and consent form or a paper version from a study team member within 24 hours. If the patient had been discharged, a paper version was mailed to the address on file.

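### Protocol 3.3 contradicts itself on navigator blinding to Tech before consent; the version was probably visible at consent, and no consent counts by version or adjustment for that selection are planned

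*Protocol*

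**What the plan says.** **Blinding.** Protocol 3.3 says of the Technology Navigators (TNs) that "TNs providing the intervention were blind to Tech assignment prior to consent, but not prior to study eligibility assessment". For patients and nurses the claim is narrower: "at the time of provisioning, both the patient and the nurse that assigned the patient the tablet were blind to Tech assignment". The statement in 3.3 about being blind at consent concerns Touch, not Tech.

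**When Tech is fixed.** Under Protocol 3.2.1, Tech is read from "the last four digits of the patient's Medical Record Number (MRN) which was assigned prior to study assignment".

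**Entry.** Protocol 5.1.1 requires that the "patient accepted tablet and use of MyChart Bedside" condition is met, and adds: "Only patients who were provisioned with MyChart Bedside were included in the study". Under 5.2, the census report was merged with the team's own records, and the stated purpose was this: "create a daily list of individuals that had consented, refused, not been provided a tablet, or were eligible for being visited by a TN". Under 5.2.1, eligible patients were invited through a link in the app, and "Interested patients were guided to the tab within MyChart Bedside that explained that participation included the following tasks and consent". A paper form was available on request.

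**What differs on screen.** Protocol 3.1.1 gives Full-Tech 10 functions, shown as side tabs, and Lite-Tech 3.

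**Checks and adjustment.** Protocol 5.4 compares age, gender, race, length of stay and Charlson index across the four arms. Protocol 3.1.3 gives the planned 60:40 Tech split and the realized split in Table 2. The SAP models containing Tech have no covariates in 1.5.1, 1.5.2, 1.6.2a, 1.6.2b, 1.7.1 to 1.7.4 and 1.8.1. Two do have one: 1.6.1 (the matching Admission item) and 1.7.5 (pre-enrollment sessions).

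**The concern.** Assignment by MRN balances the randomised patients who are provisioned. It does not by itself balance those who go on to consent, if they and the staff can see the version first. Patients holding a three-function portal might consent less often, or be recruited less actively. If those who still consent are keener on portals, Lite-Tech and Full-Tech participants differ before any outcome is measured.

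Intention-to-treat analysis of enrolled patients cannot undo selection that occurs before enrollment. The inverse-probability weights in SAP 1.4.1 apply only to the per-protocol population and model receipt of the assigned intervention, not consent. A reader who takes from 3.3 that TNs were blind to Tech until consent could wrongly dismiss staff-driven selection.

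**Working it through.** **1. Order of events.**
- The MRN, and with it Tech, exists before study assignment (3.2.1).
- The tablet is provisioned; patient and nurse are blind at that moment (3.3).
- The patient has accepted the tablet and app (5.1.1) and is listed as eligible for a TN visit (5.2).
- Staff approach the patient and guide those interested to a tab in the app (5.2.1).
- Consent is given, usually in the app.

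Eligibility comes before consent. A TN who is not blind at eligibility cannot be blind up to consent, so the sentence in 3.3 fails on its own terms. The fourth step puts patient and staff in front of a screen that differs by arm (3.1.1). That the version was open to view is a strong inference from this route; the documents do not state it.

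**2. Table 2 reproduced.** Full 624 + 1,523 = 2,147; Lite 277 + 468 = 745; total 2,892. Full share 2,147/2,892 = 74.2%. High-Touch share 901/2,892 = 31.2%.

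**3. Against the planned split.** Protocol 3.2.1 reports a simulation in which the MRN scheme "created appropriately sized groups of 40% and 60" per cent.
- Expected Full: 0.60 × 2,892 = 1,735. Expected Lite: 0.40 × 2,892 = 1,157.
- z = (0.7424 − 0.60)/√(0.24/2,892) = 15.6.
- Relative inclusion, Full to Lite: (2,147/745)/(60/40) = 1.92; Lite to Full: 1/1.92 = 0.52.

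The z value rejects a pure 60:40 sample. Protocol 3.2.1 and 4.2.1 already say that this is not one, so z is not evidence about consent.

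**4. Can the split be explained without differential consent?** Let h be the non-randomised Full-Tech patients in Table 2 and L the randomised Lite patients removed after consent, with no randomised Full patients removed. Equal consent requires (2,147 − h)/(745 + L) = 1.5, so h = 1,029.5 − 1.5L.

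| L (assumed) | h needed |
|---|---|
| 0 | about 1,030 (36% of the table) |
| 300 | about 580 |
| about 686 | 0 |

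The text gives neither h nor L. Table 2 also appears to be processed data: High-Touch is 31.2%, although Touch was never allocated below 50% (3.1.3). This fits the reassignment in 4.3, so exclusions may already have been applied.

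**5. What the existing check can see.** With 80% power and two-sided 0.05, the smallest detectable standardized difference between Tech versions is (1.960 + 0.842) × √(1/2,147 + 1/745) = 0.12. That is sensitive, but only for the five variables in 5.4. None measures prior portal use or interest in technology.

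**6. Possible size, on assumptions alone.** Suppose half of provisioned patients are portal-engaged, Full-Tech consent ignores engagement, and in Lite the engaged consent r times as often as the others. The engaged share in Lite is then r/(1 + r). If engaged patients have k times the sessions, the spurious Full:Lite session ratio is (0.5k + 0.5)/[1 + (k − 1)r/(1 + r)].
- r = 1.1, k = 1.5: 1.25/1.262 = 0.991.
- r = 1.5, k = 2: 1.5/1.6 = 0.938.

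In this scenario the bias understates a Full-Tech benefit. Consent that differs by version but is unrelated to engagement would give no such bias. Nothing in the documents fixes r or k.

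**The case against.** **The contradiction covers TNs only.** This stands. The protocol does not claim that patients were blind to Tech at consent, and the sentence itself discloses a lack of blinding at eligibility. It may be a transposed phrase. Nothing shows that patients knew another version existed, and some consented on paper. But staff and patient behaviour can respond to a sparse portal without knowledge of the other arm.

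**A reader might infer that nothing checks or adjusts for selection.** The documents do not support that. Protocol 5.4 and Table 2 are indirect checks. SAP 1.6.1 and 1.7.5 adjust for a baseline item or prior sessions, and the adoption models in 1.7.1 to 1.7.3 leave out prior MyChart users. None of these measures consent by version. Protocol 3.4 says that the CONSORT diagram shows what limited enrollment; the diagram is not available here, so whether it gives refusals by Tech version cannot be judged.

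**A reader might infer from 74:26 that Lite patients consented less often.** That does not follow. Patients with earlier Full access kept it without randomisation (3.2.1, 4.2.1); Lite patients later admitted to always-Full units were removed (4.2); users of both versions (4.2.1) and non-users (6.3.8) were excluded. Nor are 1,030 non-randomised patients required to explain the split: that figure holds only if no Lite patients were removed.

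**Data on refusers may not be usable.** This also stands. The daily list recorded refusals, but consent in 5.2.1 authorises extraction for those who signed, and no section says that refusers' records were kept or may be analysed.

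**Conclusion.** The point holds in a limited form. The sentence in 3.3 is self-contradictory, and the entry procedure strongly implies that the version was visible when most patients consented. Selection by Tech version is therefore possible and could bias Tech contrasts, most directly where the model has no covariates. The text plans neither consent or refusal counts by version nor adjustment for selection at consent.

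The size cannot be obtained from the documents. The realized 74.2% against 60% is compatible with equal consent and with markedly unequal consent, depending on h and L. It should not be read as showing bias, and still less bias in every Tech comparison under H1 to H4. The conclusion rests on in-app consent being the usual route and on the version being recognisable from its tabs.

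**What to change.** 1. Reconcile 3.3 with 5.1.1 and 5.2.1. Do not claim that TNs were blind to Tech before consent unless that can be shown; say who could see the version, and when.
2. Where retained records and ethics approval permit, report patients provisioned, approached, refused and consented by MRN-assigned Tech version, with the never-randomised Full-Tech patients shown separately. Give counts for each later exclusion by version, so that the Table 2 split can be traced.
3. Add a stated sensitivity analysis of the Tech models that now have no covariates, adjusting for age, sex, race and Charlson index, and for prior MyChart use where the outcome does not already condition on it. Length of stay is left out because it is known only after entry.
4. If entry differs by version, word the Tech conclusions as applying to patients who consented after being provisioned with their version.

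Cost: revised wording in both documents, a count table, and one further model per affected outcome. The table takes some work, since assignment must be derived from the MRN and refusal records may be incomplete. The Tech claim may weaken, and adjustment removes only selection explained by the measured covariates, so the count table is the more informative item.

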3.4 Sample size

The study did not adopt a sampling frame and represented a census approach to the implementation. The Consort Diagram (see Figure 1), provides information on the pragmatic factors that limited enrollment.

The original protocol calculated power based on 2016 Hospital Consumer Assessment of Healthcare Provider and Systems (HCAHPS) patient satisfaction scores as a baseline for outcome measures using G*Power 3.1 software. An expected enrollment of 3,872 was planned with the design expected to be sensitive enough to identify changes of between 2.2% and 3.8% across the panel of HCAHPS patient satisfaction scores.

3.5 Statistical interim analysis and stopping guidance

No interim analyses were planned or conducted for our study. Since HT2 posed minimal risk, stopping guidance was not applicable.

3.6 Timing of final analysis

HT2 was a minimal risk study, and as a result, final outcomes and their association with the interventions were reviewed only upon study completion.

3.7 Study flow

Patient participation in the study followed the CONSORT diagram shown in Figure 1.

[figure not shown]

Figure 1. CONSORT diagram.

3.8 Timing and mode of outcome assessment

The outcomes for this study included measures of use of both the inpatient and outpatient portal as well as measures of satisfaction and self-efficacy.

3.8.1 Portal usage

MyChart Bedside and MyChart usage was determined through the use of log file analysis (LFA). The methods associated with LFA have been extensively discussed in methods papers published by the research team. Log files provided the date, time, and type of interaction with each of the functions in both of the patient portals. The log file data that was available included:

1. Login date and time
2. Functions accessed
3. Activity notes

Log files were linked to the patient MRN within the Epic Clarity clinical data record. MyChart Bedside and MyChart log files were obtained in an identified form for study participants for purposes of matching this data to Admission and Post-discharge surveys and follow-up interviews (see Section 6 - Data Management).

3.8.2 Satisfaction and self-efficacy

Data on satisfaction and self-efficacy were collected via survey at enrollment (referred to as the Admission survey), between 10 and 21 days post-discharge (referred to as the 15-day Post-discharge survey) and, finally, at six months post-discharge (referred to as the 6-month Post-discharge survey). The three surveys each gathered data on the outcomes to allow for comparisons at different time points.

The Admission survey included questions related to self-efficacy, hospital satisfaction, and patient experience. The Admission survey was administered in two modes: a paper form and electronically. The electronic survey was created and collected using Qualtrics online survey software. Patients accessed the survey via the MyChart Bedside portal. The default administration mode was electronic; paper forms were only given if the patient requested it or encountered a technical issue with the hospital-issued tablet that affected their ability to complete the survey electronically.

3.8.3 Post-discharge survey administration

Both the 15-day and 6-month Post-discharge surveys were administered based on the communication preference of the participant. During the consent process, participants were asked to identify a communication preference—email or phone—through which they

would be contacted for the follow-up surveys. The study team developed a robust communication approach that would initiate contact based on stated preference, allow for participants to change their preference throughout the study, and would leverage alternate approaches if the participant could not be reached using their preferred approach. When email was used, the research team would send the participant an invitation and a link to the Qualtrics online survey and up to three reminders. When a phone call was used, the research team would attempt up to three calls. Communication efforts for Post-discharge surveys began 10 days post-discharge from the enrollment admission and 24 weeks post-discharge from the enrollment admission.

Section 4: Statistical principles

4.1 Confidence intervals and p-values

For all statistical tests, a p-value of 0.05 was used to assess significance and 95% confidence intervals were reported. No adjustments were made for multiple hypothesis testing.

4.2 Adherence and protocol deviations

The HT2 study was designed as a pragmatic study with the interventions conducted using a *per protocol* approach.

Protocol deviations

Protocol deviations may have occurred if:

1. a participant consented to participate in the study but subsequently requested a change in Tech status to the OSUWMC;
2. a participant was admitted to the OSUWMC, was assigned to the Lite intervention, and was subsequently admitted to a unit that always received the Full version of MyChart Bedside.

In these cases, the individual was removed from the study.

4.2.1 Operational protocol amendments

Operational protocol amendment 1: Improve enrollment yield (Jan 2017)

A research team member could visit the patient to remind them to complete the survey, limited to three visits per patient, once per day. Patients without completed surveys could also be visited on subsequent hospital admissions to complete their survey.

Operational protocol amendment 2: Improve data quality (Jul 2017)

A confirmation was added to each page of the survey to inform respondents when they had left questions unanswered on a page. They could continue to advance if that was their preference.

Operational protocol amendment 3: Intervention available after consent (Feb 2018)

TNs were allowed to make first contact for the High-Touch intervention once the patient consented—no longer waiting for a complete Admission survey. The TN should work with the patient to walk them through completing the survey during the intervention.

Operational protocol amendment 4: Intervention assignment (Mar 2018)

Individuals that had activated a MyChart Bedside account or were in a Full-Tech unit prior to the study start were manually assigned Full-Tech regardless of their MRN.

Individuals who were found to have accessed both Full and Lite versions over the course of the study were to be excluded from the analysis for this study.

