6.3.1 Multiple MRNs

MRNs were used as primary identifiers by both the hospital and in the context of the study. Moreover, MRNs were used throughout data processing to associate data with a unique patient. Typically, each unique patient had a single, unique MRN. In rare cases, for instance when a patient presented in the emergency room and was unable to provide identification, a patient may have been temporarily issued an MRN. While hospital records are adjusted to ensure a single, unique MRN at a later time, data was written to the log files with the temporary MRN. Patients with multiple MRNs were identified, along with their duplicate MRNs, and the identifiers were recoded to a “primary” MRN in the processed data.

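### Some participants entered Full-Tech outside the MRN randomisation and one removal rule hits Lite-Tech only, so the Tech contrast that the SAP calls intention-to-treat is not clearly a randomised comparison

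*Protocol*

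**What the plan says.** - **Randomisation.** Protocol 3.1.3 plans 60% Full-Tech and 40% Lite-Tech. Protocol 3.2.1 compares a random number table with the last four digits of the "Medical Record Number (MRN) which was assigned prior to study assignment".
- **Entry to Full-Tech outside that process.** Under Protocol 3.2.1, people with Full access before enrollment "maintained their Full-Tech status and were excluded from randomization if they were transferred to a unit included in the study". Protocol 4.2.1, amendment 4, covers those with a Bedside account or in a Full-Tech unit, who "prior to the study start were manually assigned Full-Tech regardless of their MRN".
- **Lite-only removal.** Protocol 4.2, item 2, removes from the study anyone who "was assigned to the Lite intervention, and was subsequently admitted to a unit that always received the Full version of MyChart Bedside". No rule removes Full-Tech participants who enter the same units.
- **Exclusions worded for either version.** These are a requested change of Tech (Protocol 4.2, item 1) and people "found to have accessed both Full and Lite versions over the course of the study were to be excluded from the analysis" (Protocol 4.2.1).
- **Analysis sets.** SAP 1.4.1 makes intention-to-treat by randomised group the main analysis. Its per-protocol set is those who received their randomised intervention. Neither definition mentions people whose Tech version was not randomised. Protocol 4.3 deals only with Touch reassignment.
- **Models.** SAP 1.5.1 and 1.5.2 (H1 Outcomes 1 and 2) use Tech, Touch and their interaction with no covariates.

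**The concern.** H1 is a primary hypothesis about use of MyChart Bedside, and earlier Bedside access is itself a route into Full-Tech. If the hand-placed are in the Tech contrast, part of any Full-Lite difference in H1 Outcomes 1 and 2 may reflect previous experience rather than the version. Prior Bedside access is not among the planned baseline characteristics (Protocol 5.4) or the per-protocol weighting variables (SAP 1.4.1). An imbalance would show, or be adjusted, only as far as it is correlated with variables such as age, comorbidity or length of stay.

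The Lite-only removal is a separate problem. Full-Tech can keep patients who later enter an always-Full unit and Lite-Tech cannot. That is an exclusion after assignment that depends on the arm, and it remains however the hand-placed are treated.

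The Touch-only analyses (H1 Outcome 3 and the Full-Tech sub-sample of SAP 1.4.3) are not exposed in this way. H2, also primary, has the same Tech term, but its satisfaction models adjust for the matching Admission survey item.

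**Working it through.** **Inputs.** Planned Full-Tech share 0.60 (Protocol 3.1.3). Table 2: Full-Tech 2,147 (624 High-Touch, 1,523 Low-Touch), Lite-Tech 745 (277 and 468), total 2,892.

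**1. The plan's own figure.** 2,147 / 2,892 = 74.2%, as Table 2 prints. The cells add to the margins.

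**2. Is it chance?** z = (observed − 0.6n) / √(0.24n).
- All: (2,147 − 1,735.2) / √694.08 = 15.6
- High-Touch column: (624 − 540.6) / √216.24 = 5.7
- Low-Touch column: (1,523 − 1,194.6) / √477.84 = 15.0

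Full-Tech has about 412 more people than 60:40 predicts. Chance does not explain this in either column. Table 2 appears to show Touch as received (31.2% High-Touch, although every phase assigned at least half to it), but moving people between Touch groups does not move them between Tech rows.

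**3. What could produce it?** Let r be the retention of randomised Lite-Tech divided by that of randomised Full-Tech. The documents do not give r. If the MRN process delivered 60:40 with no assignment failures, randomised Full-Tech in Table 2 is 1.5 × 745 / r = 1,117.5 / r, and the hand-placed number 2,147 − 1,117.5 / r.

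| Assumption | Hand-placed | Share of Full-Tech |
|---|---|---|
| r = 1, no failures | 2,147 − 1,117.5 ≈ 1,030 | 48% |
| r = 0.8, no failures | 2,147 − 1,396.9 ≈ 750 | 35% |
| r = 0.6, no failures | 2,147 − 1,862.5 ≈ 285 | 13% |
| r = 1,117.5 / 2,147 = 0.52, no failures | 0 | 0% |
| r = 1, with failures | 0 | 0% |

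The last row needs explanation. Protocol 1.8 reports a cohort that did not receive the intended Tech version. If Table 2 counts the version received (not stated), about 412 of an expected 0.4 × 2,892 = 1,157 Lite-Tech people (36%) given Full-Tech would reproduce the table with equal retention and nobody hand-placed. The rows are illustrations, not bounds, and mixtures are possible.

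**4. Size of bias.** If a share h of Full-Tech is hand-placed and their rate on a binary outcome differs by d from that of randomised Full-Tech, the Tech difference shifts by h × d. Neither is given. With assumed values, h = 10% and d = 5 points give 0.5 point, and h = 48% and d = 20 points give 9.6 points. That range is too wide to count as an estimate.

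**5. Are the hand-placed in the analysis?** Protocol 3.2.1 takes them out of randomisation, and SAP 1.4.1 analyses by randomised group. Together these could leave them out. Protocol 4.2.1, however, assigns them to an arm, and neither Protocol 6.3.8 (additional exclusions) nor any other readable section excludes them. The text does not settle the question.

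**6. Which people?** Protocol 3.2.1 dates prior access from enrollment, and Protocol 4.2.1 from the start of the study. The groups may overlap, but the dates do not define the same set.

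**The case against.** The strongest reply is that the plan already excludes these people: whoever was not randomised on Tech cannot be analysed by randomised Tech group. On that reading the defect is a missing sentence and missing counts. The counts may be in the CONSORT figure, which is not shown in the text available ("Patient participation in the study followed the CONSORT diagram shown in Figure 1"). Protocol 4.2 also says only that the listed deviations may have occurred, and gives no number.

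Part of this stands. The documents do not show that the hand-placed are in the Tech contrast, and the missing figure cannot be held against the plan. But exclusion is an inference that Protocol 4.2.1 does not support, and it leaves the Lite-only removal untouched. People removed from the study cannot be analysed as randomised whatever they went on to receive, which is what SAP 1.4.1 promises.

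A reader might infer from Table 2 that about half of Full-Tech was never randomised, or that Lite-Tech must have been retained at 52% of the Full-Tech rate if nobody was hand-placed. The documents support neither. Both figures assume that the MRN process delivered 60:40, and Protocol 1.8 reports that for some participants it did not.

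**Conclusion.** The point holds and should be fixed before the Tech results are read as intention-to-treat. Three things are firm: a non-random route into Full-Tech, a removal rule for Lite-Tech only, and an SAP population that does not place people who were never randomised on Tech. The Lite-only removal conflicts with intention-to-treat on either reading. The hand placement threatens H1 Outcomes 1 and 2 if those people are included.

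The departure from 60:40 (74.2%, z = 15.6) is certain, but its cause is not. Table 2 does not show that hand placement produced it, and the size and direction of any bias cannot be computed from the documents.

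**What to change.** In SAP 1.4.1 and 1.4.2:

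1. First reconcile Protocol 3.2.1 and 4.2.1 on the date that defines prior Full access (enrollment or study start). The next step cannot be applied until this is settled.
2. Base the main Tech and Tech*Touch estimates on everyone who did not meet the prior-access rule. Apply the rule in the same way whichever version the MRN would have given. Analyse by MRN-assigned version whatever was delivered, so that the mis-delivered cohort of Protocol 1.8 stays in. Give the full set as a sensitivity analysis.
3. For intention-to-treat, keep people removed or excluded after assignment (both items of Protocol 4.2, and use of both versions) in their MRN-assigned arm where usable data exist. Otherwise report their numbers by arm.
4. Keep the hand-placed in the Touch estimates, since "Participants were randomized into each arm of each intervention, Tech and Touch, in separate processes". Either estimate Touch on the full set separately from Tech, or add a manual-placement indicator, with indicator*Touch in the interacted model. In the additive model the indicator separates the groups only approximately: in a least-squares check with 1,030 hand-placed, their cells keep weights of ±0.028 in the Tech estimate.
5. Report the numbers hand-placed, removed, excluded and mis-delivered, by MRN-assigned version.

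**Cost.** This needs SAP wording and a re-run. Protocol 1.8 says that Tech assignment was already reconstructed with the original code. If about 1,030 people leave the Tech contrast, its standard error rises by √(1/1,117.5 + 1/745) / √(1/2,147 + 1/745) = 0.0473 / 0.0425 = 1.11, about 11%. With 750 it rises by about 7%. If the hand-placed split across Touch like the rest of Full-Tech, the Tech*Touch standard error rises by about 12% with 1,030. Dropping them from Touch as well would raise its standard error by about 23%; with the indicator it does not change. These figures are unadjusted, assume independent errors and ignore clustering by hospital. The planned negative binomial and logistic models will differ somewhat. Data for removed people may be incomplete, so step 3 may be only partly possible.
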